4.3.3. Per Protocol Set (PPS)

The PPS will include all randomized patients who are included in the FAS, provided they:

- Meet all inclusion criteria affecting the evaluation of efficacy
- Meet no exclusion criteria affecting the evaluation of efficacy
- Do not have any major protocol deviations affecting the evaluation of efficacy (as defined in the Study Deviation Rules Document)
- Do not use any prohibited therapy affecting the evaluation of efficacy during the study

The criteria above represent an adherence to the specifications of the protocol with regards to efficacy assessments. The details of the rules used to make the determination of which criteria affect the evaluation of efficacy will be provided in a separate document that will be reviewed by study personnel at the sponsor. The first version of this Study Deviation Rules Document will be completed and signed off prior to the first patient being randomized. This document will be finalized prior to unblinding. Patients who receive any dose of the incorrect study drug will not be included in the PPS. Prohibited therapies will be assessed by a medical review to determine whether they affect the evaluation of efficacy. This review will be finalized prior to final unblinding.

Presentations based on this set of patients will group them according to their randomized treatment. Supplementary analyses will be performed on the PPS. Patients in the FAS who fail to meet these criteria for entry in to the PPS will be listed with their reason(s) for exclusion from the PPS.

4.3.4. Safety Population

The safety population will include all randomized patients who receive at least 1 dose of study drug. Presentations based on this set of patients will group them according to the first study treatment they are administered.

4.3.5. PK Concentration Population

The PK concentration population will include all patients who receive at least 1 dose of S-600918 and have at least 1 evaluable concentration. Presentations based on this set of patients will group them according to the treatment received.

5. Patient Disposition

5.1. Disposition

Among patients randomized, the number and percentage of patients who complete the study and who withdraw from the study, as well as the reasons leading to withdrawal, will be summarized by treatment group. Also, among all randomized patients, the number of patients included in each analysis population defined in section 4.3 will be summarized by treatment group, as well as overall. As well as randomized patients, patients withdrawn from the study during screening period will be tabulated by reason of withdrawal and listed.

5.2. Protocol Deviations

Protocol deviations that are relevant to the analyses will be identified in a separate protocol deviations rules document that will be reviewed by study personnel. During the study, these rules will be reviewed and instances where patients met any of the conditions will be logged in a database that will be finalized and locked prior to final unblinding. Major deviations, that is those that are related to efficacy, will inform the per protocol set (PPS) as described in section 4.3.3. In addition to these major deviations that result in the removal of patients from the PPS, the significant protocol deviations, that are required for CSR reporting, will be summarized and listed.

5.3. COVID-19 / SARS-COV-2

Shortly after this study began enrolling patients, the SARS-COV-2 virus, which causes coronavirus disease 2019 (COVID-19) was declared a global pandemic by the World Health Organization. In accordance with guidances issued by regulatory agencies, study data collection has been amended for randomization patients to capture visits missed due to COVID-19 related reasons, and discontinuations due to COVID-19 related reasons. COVID-19 related adverse events, concomitant medications, and medical history are collected using existing CRFs.

Listings of patients who missed visits due to COVID-19 related reasons will be listed for the All Randomized Population. Patients who withdraw from the study due to COVID-19 related reasons will be summarized and listed as described in section 5.1 Disposition, of this SAP.

The anticipated impact of COVID-19 is widely regarded as unknown. If the impact of COVID-19 on the conduct of this study is observed to be significant, further summaries and listings of the impact will be explored.

6. Demographics and Baseline Characteristics

All summaries of demographics and baseline characteristics described in this section will be presented for the FAS and for the Safety Population.

6.1. Demographics

A summary of demographics and baseline information will be presented by treatment group. The demographic characteristics consist of age (years) at informed consent, sex, race, and ethnicity. The

baseline characteristics consist of baseline height (cm), baseline weight (kg), and baseline body mass index (BMI) (kg/m²). Body mass index is calculated as (body weight in kilograms) / (height in meters)².

Age, along with height, weight, and BMI at baseline, will be summarized using descriptive statistics. The number and percentage of patients by age category (<45, $\geq45 - <65$, ≥65), sex (Male, Female), race (White, Black or African American, Asian, American Indian or Alaska Native, Native Hawaiian or Other Pacific Islander, and Other), ethnicity (Hispanic or Latino, Not Hispanic or Latino), and region (Japan, Europe, and United States) will also be summarized.

Patient demographic and baseline characteristics will also be presented via listings.

6.2. Baseline Disease Characteristics

Average cough counts per hour in 24 hours at Visit 1 and Visit 2 and baseline will be summarized using descriptive statistics by treatment group. In addition, the weekly severity of cough (VAS) at baseline, the LCQ at baseline, and baseline pulmonary function test results, including FVC (L), FEV1 (L), and FEV1/FVC ratio will be summarized using descriptive statistics. As well, the duration of chronic cough (months; ((date of screening – reported start date of chronic cough) + 1) / 30.4375) will be summarized using descriptive statistics by treatment group. When part of the start date or end date is missing, 15^{th} of the month for missing day and July 1^{st} when month and day are missing will be used.

Cough-related history will be recorded on the eCRF and coded using MedDRA v22.1. The number and percentage of patients with any cough-related history will be summarized by treatment and overall for each preferred term. Cough-related history will also be listed with the calculated duration of each history. For the calculation of duration, partial dates will be handled as above, using the 15th of the month for missing day and July 1st when month and day are missing. Ongoing histories will use the date of enrollment as the end date for calculating duration.

6.3. Smoking History

Smoking history (pack-years) will be summarized categorically (0 pack-years, > 0 pack-years, > 5 pack-years, >10 pack-years, and >15 pack-years), and using descriptive statistics by treatment group.

6.4. Medical History

Medical history, including prior and current conditions, surgeries, cough-related history, alcohol use, smoking, and marijuana use will be recorded on the eCRF and coded using MedDRA v22.1. The number and percentage of patients with any medical history will be summarized by treatment and overall for each system organ class and preferred term. Medical history data will also be presented in a listing.

6.5. Inclusion and Exclusion Criteria

Randomized patients that fail to meet eligibility criteria will be listed with the inclusion or exclusion criteria that was not met.

7. Treatments and Medications

7.1. Prior, Concomitant, and Restricted Medications

Prior, concomitant, and restricted medications and therapies will be coded using the WHO Drug Dictionary. Prior medications will be classified as those medications that begin prior to the first

administration of study drug. Concomitant medications are those medications that may have been taken during study treatment. This principle applies to medications for which partial or missing start or end dates are recorded. Restricted therapy is defined as any concomitant therapy for which use is permitted only with restrictions.

For the purposes of classifying a course of treatment as prior and/or concomitant, partial start dates will be presumed as the earliest possible recorded date. Start dates that are entirely missing will be presumed as the date of informed consent.

For the purposes of classifying a course of treatment as prior and/or concomitant, partial end dates will be presumed as the latest possible recorded date. Records with end dates that are entirely missing will be considered as prior and concomitant if the start date occurs before study treatment. Such records with start dates occurring after the first dose of study treatment will be considered concomitant.

7.1.1. Prior Medications

The number and percentage of patients using any prior medications and by preferred term will be summarized by treatment for the FAS and the Safety Population. Prior medications will be listed for the Safety Population.

7.1.2. Concomitant Medications

The number and percentage of patients using any concomitant medications and by preferred term will be summarized by treatment for the FAS and the Safety Population. Concomitant medications will be listed for the Safety Population.

7.1.3. Restricted Medications

The number and percentage of patients using any restricted medications and by preferred term will be summarized by treatment for the FAS and the Safety Population. Restricted medications will be listed for the Safety Population.

7.2. Study Treatments

7.2.1. Study Drug Exposure

Duration of exposure is defined as the total number of days a patient is exposed to any study drug and will be presented as the total number of days from the first dose date (Day 1) to the last dose date (date of last dose minus the date of first dose + 1) as recorded in the clinical database. If a patient is lost to follow-up, but the drug accountability log confirms that the patient has taken study drug, the visit date following the last completed drug accountability log will be used. If drug accountability log is missing for some reason, the patients will be regarded as not dosed for such duration.

The duration of exposure to study drug by treatment will be summarized by treatment for the FAS and the Safety Population using descriptive statistics. The duration of exposure will then be classified into one of the following categories: > 1 day, >= 7 days, >= 14 days, >= 21 days and >= 25 days and will be presented as the number and percentage of patients in each duration category.

The cumulative dose will be defined as the sum of the actual dose across all study days on which study drug was taken. Patients who take more or less than the planned 6 tablets of study drug in a day will be considered to have received actual dose of (# of tablets taken / 6) for that day. Average daily dose is the cumulative dose divided by the duration of exposure. The average daily dose and cumulative dose will be summarized by descriptive summary statistics.

A summary of each patient's exposure will be presented in a listing.

7.2.2. Treatment Compliance

Overall study drug compliance will be calculated for each patient by evaluating how many days a patient takes study drug as directed while on study treatment up to and including Day 28. For each day on treatment, the number of tablets taken will be directly captured on the eCRF. Days where 6 tablets are recorded as taken will be counted as the number of days of compliant dosing until the earliest date of day after the date of V6, Day 28 or date prior to the date of discontinuation. For patients who complete treatment, the number of days on treatment will be calculated as (day after the date of Visit 6 – date of Visit 3) + 1. For patients who prematurely discontinue treatment, the number of days on treatment will be calculated as (date prior to the date of discontinuation – date of Visit 3) + 1. The number of days on treatment will be considered up to Day 28 – that is, the number of days on treatment will have a maximum value of 28.

Thus, the overall study drug compliance (%) will be calculated as:

Compliance = $100 x \frac{Number of Days of Compliant Dosing}{Number of Days on Treatment}$

Where number of days on treatment is defined as in section 7.2.1. A patient is considered to have demonstrated adequate compliance if overall study drug compliance is between 80% and 100%, inclusive.

A categorical summary of whether patients were compliant (yes/no) will be presented by treatment group for the safety population. Summary statistics on percentage of treatment compliance as well as the number and percentage of patients in each compliance category (>=70%, >=80%, >=90%, 100%) will be presented by treatment group for the safety population.

8. Efficacy Analysis

For all efficacy analyses, baseline is defined the last assessment before first dose of study drug, unless otherwise noted. All efficacy analyses will be presented for FAS, and, where noted, for the PPS. When the framework described for the primary analysis (which is also used in several subsequent analyses) is applied to cough count data, if any patient has an average coughs per hour at any baseline or post-baseline measurement that is zero, a correction factor of 0.1 will be added to all observed average coughs per hour values for all patients. A correction factor of 0.1 is necessary because these counts are log-transformed for the purposes of analysis, and log₁₀(0) is undefined. This handling is applied in the same manner to average coughs per hour in 24 hours, while asleep, and while awake. In principle, efficacy analyses will be based on data compliant with the analysis visit window at each visit in the treatment period for both of FAS and PPS (see section 4 of this SAP). For this reason, data outside the analysis visit windows will be regarded as missing.

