9.10.3 Analyses of Efficacy Endpoints

For analyses of all efficacy endpoints unless otherwise noted, baseline is defined as Visit 2. All efficacy endpoints will be summarized by visit. The analysis window for the primary endpoint will be defined in the SAP and may not match the visit window in the protocol. The number of coughs (including cough counts by waking and sleeping hours [see Section 7.4.1]) will be provided by cough analysis technicians to the sponsor.

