3.4. Dose Adjustment/Modifications

No dose adjustments or modifications are allowed in this study.

4. General Statistical Considerations

Unless otherwise noted, continuous variables will be summarized based on the number of non-missing observations (N), arithmetic mean (Mean), standard deviation (SD), median, minimum, and maximum values. Categorical variables will be summarized based on the frequency count and the percentage of patients in each category. All statistical tests will be performed at the 0.05 significance level using 2-sided tests, unless otherwise noted, and statistical testing will not be adjusted for multiple comparisons.

Study data will be presented in by-patient data listings. In general, all tables will be presented by treatment group. Individual patient data, PK data, and any derived data will be presented by treatment group (study drug) (S-600918 50 mg, S-600918 150 mg, S-600918 300 mg, and placebo). All analyses and tabulations will be performed by using SAS Version 9.2 or higher and WinNonlin Version 6.3 or higher.

Baseline will be defined as the last valid assessment recorded prior to the first administration of study drug unless otherwise specified.

For summaries, patients will be counted only once within each planned visit. In these summaries, the visit windows will follow the windows given in the protocol, which are repeated in Appendix 1 of this SAP. However, +1 day will be allowed at the end of the Visit 6 time window for analysis.

Visit	Target Day	Window Start Day	Window End Day
Visit 1 / Screening	-18	-28	-18
Visit 2 / Day -1	-1	-1	-1
Visit 3 / Day 1	1	1	1
Visit 4 / Day 8	8	6	10
Visit 5 / Week 3	22	20	24
Visit 6 / Week 4	27	25	28

Table 4-1: General Analysis Visit Wind

In the event that more than one observation is recorded within one of these windows, then, among these records within the window, the record occurring at the planned visit in the CRF will be used. If no records occurred at the planned visit within the window, then records occurring at any unplanned visits within the visit window will be considered, and the record occurring closest in time to the target visit day will be used. Results that are recorded at an Early Discontinuation visit may be summarized at a planned visit if the Early Discontinuation visit falls within the window for the planned visit, and the planned visit has not occurred.

Study days will be calculated using the date of the first administration of study drug as follows:

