8.1.2. Sensitivity Analyses of the Primary Endpoint

A sensitivity analysis of the primary efficacy endpoint will be performed on the FAS using an analysis of covariance containing treatment group, as factor; and region and the common logarithm of the frequency of coughs per hour at baseline as covariates. It is expected that this ANCOVA will perform similarly as the primary analysis, using the observed data. Thus, two sensitivity analyses using this ANCOVA model on the FAS will be performed: one that imputes missing observations with the last post-baseline observation, and that imputes the baseline cough counts per hour for missing observations.

Furthermore, the primary analysis will be repeated for the FAS using 1) the protocol visit windows found in Table 7-2 of the Protocol, and 2) the nominal visit analysis windows presented below in Table 8-1.

Visit	Target Day	Window Start Day	Window End Day
Visit 1	-18	-28	-18
Visit 2	-1	-1	-1
Visit 3	1	1	1
Visit 4	8	2	14
Visit 5	22	15	24
Visit 6	27	25	Latest of Day 28, Day of Visit 6, and Day of Last Dose of Study Drug

Table 8-1: Analysis Visit Windows for Sensitivity Analysis

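### The baseline-carried-forward ANCOVA overwrites Visit 6 cough recordings that were observed after Day 28, so it mixes late visits with missing data

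*SAP*

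**What the plan says.** SAP section 4 states that "the visit windows will follow the windows given in the protocol" and then that "1 day will be allowed at the end of the Visit 6 time window for analysis". Table 4-1 accordingly gives Visit 6 as Days 25 to 28. SAP section 8 applies these windows, in principle, to efficacy analyses on both the FAS and the PPS, and adds that "data outside the analysis visit windows will be regarded as missing".

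SAP 8.1.2 plans two kinds of sensitivity analysis for the primary endpoint:

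- **Imputation.** There are two ANCOVAs on the FAS: "one that imputes missing observations with the last post-baseline observation" and another that "imputes the baseline cough counts per hour for missing observations". No visit window is stated for either.
- **Window.** The primary analysis, that is the mixed model, is repeated with "the protocol visit windows found in Table 7-2 of the Protocol" and with the windows of SAP Table 8-1. In Table 8-1 the Visit 6 window closes at the "Latest of Day 28, Day of Visit 6, and Day of Last Dose of Study Drug".

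SAP 8.1.3 repeats the same set on the PPS. Protocol 9.10.3 leaves the analysis window for the primary endpoint to the SAP and warns that it "may not match the visit window in the protocol".

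**The concern.** A BOCF analysis is meant to show how far the result could move if the values that nobody observed were unfavourable. Here the set called missing also contains values that were observed, only too late for Table 4-1. For those patients a measured Week 4 cough rate is discarded and a ratio of 1 (log ratio 0) is put in its place.

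The SAP foresees late visits. Table 8-1 extends to the actual day of Visit 6, and SAP 7.2.2 caps the compliance period at Day 28 in case the day after Visit 6 falls later. Protocol 5.6 provides three spare days of drug per wallet.

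If BOCF and the primary analysis disagree, a reader could not tell whether missing data or late visits caused the gap. If the share of late visits differs by arm, the discrepancy could go either way.

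**Working it through.** **1. Which recordings are affected.** SAP section 4 counts study day as date minus first-dose date plus 1. Table 4-1 ends Visit 6 at Day 28, so a recording from Day 29 on is missing under SAP section 8.

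| Analysis (SAP 8.1.1 and 8.1.2) | Visit 6 window | What happens to a Day 29+ recording |
|---|---|---|
| Primary mixed model | Table 4-1 | Left out, not imputed |
| Mixed model, Table 8-1 rerun | Table 8-1 | Used |
| LOCF ANCOVA | None stated, so Table 4-1 | Replaced by an earlier visit, if section 8 is followed |
| BOCF ANCOVA | None stated, so Table 4-1 | Replaced by baseline |

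The LOCF row is less certain. Read without section 8, the last post-baseline observation could be the late recording itself.

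**2. The plan's own figure.** Protocol 9.2 and SAP 4.1 give a difference of -0.163 and SD of 0.371 on the log10 ratio, two-sided 5%, 80% power. The two-sample t calculation gives 83 per group (power 80.3%). 83/0.90 rounds up to 93, and 4 × 93 = 372. This reproduces. The planned effect is 1 - 10^(-0.163) = 31.3% reduction versus placebo.

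**3. Size of the BOCF shift.** Inputs: placebo mean -0.160 (proof-of-concept study, protocol 9.2); active mean -0.160 - 0.163 = -0.323. The late share m is not in the documents. I assume 5% or 10%, which is 4.7 or 9.3 of 93 patients per arm. BOCF sets the log ratio of late patients to 0, so

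difference = -0.323 × (1 - m_active) + 0.160 × (1 - m_placebo); reduction = 1 - 10^difference.

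| Late on active | Late on placebo | Difference | Reduction shown |
|---|---|---|---|
| 0% | 0% | -0.163 | 31.3% |
| 5% | 5% | -0.155 | 30.0% |
| 10% | 10% | -0.147 | 28.7% |
| 10% | 5% | -0.139 | 27.3% |
| 5% | 10% | -0.163 | 31.3% |
| 0% | 5% | -0.171 | 32.5% |
| 0% | 10% | -0.179 | 33.8% |

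These are differences in unadjusted means. The calculation isolates the late visits and assumes no other missing data.

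**4. Power of the BOCF comparison, equal late rates.** Variance per arm = (1 - m) × 0.371² + m(1 - m) × mean². Averaged over the two arms, the SD is 0.366 (5%) or 0.360 (10%). At 93 per arm, power falls from 84.6% to 81.9% or 78.9%. At 83 per arm, it falls from 80.3% to 77.4% or 74.2%.

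**5. LOCF.** If the Visit 5 effect is a fraction f of the Visit 6 effect, the difference is -0.163 × (1 - m(1 - f)). With m up to 10% and f from 0.8 to 1.0, this runs from -0.160 to -0.163, a reduction of 30.8% to 31.3%.

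**The case against.** The strongest reply is that SAP 8.1.2 varies one thing at a time. The ANCOVAs keep the primary window and change how missing values are handled; the window reruns keep the model and change the window. On that view a sensitivity analysis should use the primary analysis's own definition of missing, and using Table 8-1 in the ANCOVAs would change two things at once. The point is fair. It is met by taking the planned Table 8-1 mixed-model rerun as the comparator, because that rerun keeps the same late Visit 6 recordings.

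Three further points stand and limit the claim. The late rate is assumed. BOCF is deliberately conservative and has no power target of its own. The in-principle wording in SAP section 8 leaves room for exceptions, although none is stated for these ANCOVAs.

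A reader might infer more than the documents support:

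- **That BOCF must pull toward no effect.** This holds for equal late rates, but the table above shows no net shift or an enlarged difference when placebo patients are late more often.
- **That the overwritten values are on-drug values.** The last dose is due the day after Visit 6 and wallets carry spare days, so many could be. But Table 8-1 has no on-drug condition, and a Visit 6 held after the last dose would also count.
- **That the Visit 6-only secondary endpoints are compromised.** No window rerun is written for them, but that is a prespecified scope choice. Reruns there would be optional, and other secondary mixed models also lack one.
- **That the Table 7-2 rerun has no defined Visit 6 window.** The Visit 6 row gives both Day 27 and four weeks after Visit 3 (1 + 28 = Day 29). However, Appendix 1 of both documents, SAP 3.2.1 and Table 4-1 all read it as Day 27. This is a wording discrepancy to reconcile.

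**Conclusion.** The point holds, and it is minor. As written, the BOCF ANCOVA replaces observed Visit 6 recordings from Day 29 onward with baseline, and no planned version of that ANCOVA uses the observed value. Its result therefore mixes lateness with missingness. At equal late rates of 5% or 10%, the effect shown drops by 1.3 or 2.6 percentage points (31.3% to 30.0% or 28.7%); with unequal rates the size and direction depend on the arm. LOCF needs a clearer definition, but its numbers hardly change.

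A reader might take this as a criticism of the primary result. It is not: the primary mixed model imputes nothing, its window is prespecified as protocol 9.10.3 allows, and the Table 8-1 rerun already tests the cut-off. The sizes rest on the assumed late rates and on the proof-of-concept means and SD used for planning.

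**What to change.** In SAP 8.1.2, state that LOCF and BOCF apply only to patients with no accepted Visit 6 recording in the Table 8-1 Visit 6 window, that the observed value is used otherwise, and that these two ANCOVAs are to be read against the planned Table 8-1 mixed-model rerun. This also settles what LOCF does with a late recording. Leave the Table 4-1 window for the primary analysis unchanged.

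The cost is one sentence, placed before unblinding, with no new data. The downside is wider timing of the Week 4 value in these sensitivity analyses. That may include recordings made after the last dose, which should be flagged in the output.

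Separately, reconcile the Visit 6 row of protocol Table 7-2 with Appendix 1, as a wording correction only.
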